9. Subjects involved in litigation regarding injury or worker's compensation benefits.	9. History, self-report
10. Subjects with a diagnosis of vasculitis, peripheral vascular disease, peripheral neuropathy, small-fiber neuropathy, or fibromyalgia.	10. Medical history, self-report.

Subject Screening:

Subjects will be referred to the study from the Addiction Institute Opioid Treatment Program. Subjects will also be recruited by word of mouth, fliers, newspaper advertisements, and postings on relevant websites. Contact information will be provided so that potential subjects may speak with a research coordinator/research assistant to learn more about the opportunity to participate in the study. Potential participants will take part in a brief phone interview to establish pre-eligibility. Pre-eligible participants will be given an appointment for a screening visit.

They will then undergo additional screening for the study, including a SCID, review of metal implants, pregnancy test (if indicated), medical history, physical exam, vital signs (HR, BP, temp), TASS, and consent for study procedures. For all females of child-bearing potential, a pregnancy test will be repeated prior to beginning rTMS sessions. Daily medication use will be assessed for the 4 weeks prior to study entry using the time-line follow back procedure.

Following screening, the subjects will undergo the following procedures:

- 1) Pregnancy tests will be performed weekly during rTMS and before each MRI. Before the rTMS begins, we will perform an initial determination of motor threshold. Subjects with a motor threshold of 85% (of maximal stimulator output) at the initial determination of motor threshold will be removed from the study. The rationale for this is that, in our experience, high motor thresholds of this level result in discomfort and anxiety when the actual rTMS sessions are delivered.
- 2) Volumetric MRI and MRS scans.
- 3) Baseline neuropsychological testing, including pain scales.
- 4) Five weeks of rTMS, Monday – Friday, on an outpatient basis. The pain scales will be performed during the weeks of rTMS, up to daily.
- 5) Repeat volumetric MRI and MRS scans after the rTMS.
- 6) Repeat neuropsychological tests after the rTMS.

Neuropsychological scales and tests: Subjects will be asked to complete the following tests and scales before and after the sessions of rTMS (at baseline and after the completion of the rTMS).

Scales (expected to take 60 minutes total):

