1. Brief Pain Inventory (at baseline and daily before each rTMS session)
2. PEG scale (at baseline and weekly before each rTMS session)
3. PROMIS-29 pain intensity and pain interference items (at baseline and weekly before each rTMS session)
4. Hamilton Depression Rating Scale (at baseline and weekly)
5. Barratt Impulsiveness Scale (BIS -11) (at baseline)
6. Columbia Suicide Severity Rating Scale (at baseline and weekly)
7. Young Mania Rating Scales (at baseline and weekly)
8. Patient-rated clinical global impression (CGI) scale (at baseline and weekly)
9. Clinician-rated CGI scale (at baseline and weekly)
10. Clinician-rated CGI-opioid scale (at baseline and weekly)
11. Clinical Opiate Withdrawal Scale (COWS) (at baseline and weekly)
12. Quality of Life Enjoyment and Satisfaction Questionnaire (Q-LES-Q) (at baseline and weekly)

Medication use: Subjects will be asked to provide to us the number of medications they took as follows: 1) at baseline (in the week prior to starting sessions); and 2) at each session, where we will ask about opioid and other medication use since the previous session. The amount of opioids used will be converted to oral morphine equivalents and tallied for each day.

Repetitive Transcranial Magentic Stimulation (rTMS): The participants will be randomized into 2 groups: 1) high frequency rTMS (20 Hz), 2) and sham treatment. The rTMS will be administered using the TMS system provided by Brainsway (Brainsway, LTD, Jerusalem, Israel). The rTMS system is equipped with a positioning and cooling system. The positioning system includes a helmet that comprises the coils (which will be either the sham or the H coil), an adjustable arm connected to the helmet, and a device enabling rotation of the helmet around three orthogonal rotation axes. The positioning device enables the accurate and comfortable placement of the coil over the patient's head. The cooling system is designed to maintain ambient temperature in the coils during repetitive operation by allowing streamed the cooled air into the helmet and maintains the coils at ambient temperature.

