- Practical demonstration of ability to perform several determinations (at least 5) of the resting motor threshold, under the direct supervision of a physician investigator experienced in rTMS.
- Performing at least the first two rTMS study sessions under the direct supervision of a physician investigator experienced in rTMS.
- Working knowledge of the principles and practices of rTMS and the rTMS device being used in the study, including common side-effects and how to recognize them. Knowledge will be based on completed tutorial sessions with the investigators or rTMS consultant experienced in rTMS.
- Knowledge how to contact the covering physician available in the building.
- Knowledge of seizure first aid, the location of the emergency equipment and medication, how to engage the emergency response system.
- Bachelor's degree or higher.

In addition, a physician with the following qualifications will be readily available in the vicinity if the need arises (in the institute, and immediately available).

Post-treatment Follow-up

Participants will return at 2 weeks and 4 weeks after completion of rTMS for the following measures:

1. Self-reported methadone dose adjustments/changes and other substance use

2. Brief Pain Inventory
3. PEG scale
4. PROMIS-29 pain intensity and pain interference items
5. Hamilton Depression Rating Scale
6. Hamilton Anxiety Rating Scale
7. Patient-rated clinical global impression (CGI) scale
8. Clinician-rated CGI scale
9. Clinician-rated CGI-opioid scale
10. Quality of Life Enjoyment and Satisfaction Questionnaire
11. Visual Analogue Scale (VAS) for Opioid Craving

Statistical Analysis:

The primary effectiveness outcome measure will be proportion of subjects who achieve $\geq 50\%$ reduction in average pain score as measured by VAS and no significant increase in opioid medication use [defined as greater than 25% increase in morphine equivalent dose].

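### The 50% pain-reduction outcome has no planned multi-day baseline and no defined baseline or end value; averaging several pre-stimulation ratings would be a cheap, modest gain in precision

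*Combined protocol and SAP*

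**What the plan says.** Under Statistical Analysis, "The primary effectiveness outcome measure will be proportion of subjects who achieve" a reduction of at least 50%, given as a "reduction in average pain score as measured by VAS and no significant increase in opioid medication use". The opioid component is failed by a rise of more than 25% in morphine equivalent dose.

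Pain measurement is described in three places:

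- Subject Screening lists a single pre-treatment step, "Baseline neuropsychological testing, including pain scales". For the treatment period it says: "The pain scales will be performed during the weeks of rTMS, up to daily". Treatment is "Five weeks of rTMS, Monday – Friday, on an outpatient basis".
- Neuropsychological scales and tests, scale 1, is the "Brief Pain Inventory (at baseline and daily before each rTMS session". The PEG and PROMIS-29 pain items are scheduled at baseline and weekly.
- Post-treatment Follow-up repeats these pain scales at 2 and 4 weeks. The only VAS in any assessment list is here: "Visual Analogue Scale (VAS) for Opioid Craving".

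No pain diary or run-in is described. No sentence says which ratings make up the baseline or the end value. Medication use, the other half of the composite, is treated differently: its baseline is the week before sessions start, and a daily history covers the 4 weeks before study entry.

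**The concern.** A percent-reduction rule uses the baseline twice: as the starting level and as the yardstick. A subject rated on an unusually bad day needs less true improvement to reach 50%; one rated on a good day needs more. Averaging many ratings during treatment does nothing to remove that error.

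The schedule is lopsided in this respect. It allows a precise end value but provides few ratings from which to build the baseline, and does not tell the analyst to average even those. Misclassification then blurs the active-sham contrast in a small study. Baseline ratings that are not collected cannot be recovered once stimulation has started.

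**Working it through.** **No figure to reproduce.** The documents give no sample size, power, expected responder rates or pain variability. What follows shows direction and rough size only.

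**Ratings available.** 5 weeks × 5 days = 25 sessions, so up to 25 pre-session BPI ratings. The first is taken before any stimulation. Pre-stimulation: the baseline step plus the pre-session-1 rating. After stimulation has begun: 25 − 1 = 24.

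**Error at the cut.** A subject responds if E ≤ 0.5·B, where E is the end value and B the baseline. With day-to-day SD s, kb independent baseline days and ke independent end days, the error variance of E − 0.5·B is s²(1/ke + 0.25/kb).

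- ke = 5, kb = 1: 0.20 + 0.25 = 0.45 s²; baseline share 0.25/0.45 = 56%.
- ke = 5, kb = 2: 0.20 + 0.125 = 0.325 s².
- ke = 5, kb = 5: 0.20 + 0.05 = 0.25 s².
- ke = 1, kb = 1: 1 + 0.25 = 1.25 s²; baseline share 0.25/1.25 = 20%.

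**Simulation.** All inputs are assumptions: ratings rounded and limited to 0-10, true baseline mean 6, s = 1.5, independent days, end value the mean of five ratings, 400,000 subjects per cell.

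| True reduction | Error | 1 baseline rating | 2 | 5 |
|---|---|---|---|---|
| 30% | false responder | 13.0% | 8.7% | 6.6% |
| 40% | false responder | 29.4% | 25.3% | 23.3% |
| 60% | missed responder | 26.9% | 24.3% | 20.1% |

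Share of the one-to-five gain already obtained with two ratings: (13.0 − 8.7)/(13.0 − 6.6) = 67%; (29.4 − 25.3)/(29.4 − 23.3) = 67%; (26.9 − 24.3)/(26.9 − 20.1) = 38%.

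**Sensitivity, one versus five baseline ratings, in the order of the table:**

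- s = 1.0: 4.9% v 1.3%, 21.4% v 14.5%, 17.8% v 10.5%.
- s = 1.5, day-to-day autocorrelation 0.8: 22.0% v 21.1%, 35.6% v 35.1%, 33.1% v 32.6%.
- s = 1.5, independent days, end value a single rating: missed responders at a true 60% reduction go slightly the wrong way on this rounded scale, 30.8% v 33.8%.

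**A mixed population.** Assume true baseline mean 6.5 (SD 1.5) and true fractional reduction mean 0.30 (SD 0.30), so about 25% are true responders. With s = 1.5, independent days and a five-rating end mean, total misclassification is 13.1%, 11.3% and 10.0% with one, two and five baseline ratings. With assumed true responder rates of about 8% (sham) and 37% (active), 80% power at two-sided 0.05 needs about 43, 40 and 38 per arm, against 32 with no measurement error. If the end value is one day, or autocorrelation is 0.8, going from one to five baseline ratings removes only about 0.2 to 1.2 points of misclassification over s from 0.5 to 2.0.

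**The case against.** Four stronger readings are tempting, and the documents do not support them.

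- **That pain is rated only once before treatment.** The BPI line itself schedules a rating before session 1, ahead of any stimulation. Nor does the text say that the baseline is one day; for medication use, baseline means a week. The already scheduled second rating yields roughly 40% to 70% of the available gain in the simulation.
- **That the BPI baseline rating is the denominator.** The outcome is a "reduction in average pain score as measured by VAS", and no pain VAS is scheduled. The link from the BPI to the primary outcome is therefore an inference.
- **That each rating is a single noisy day.** The documents give no recall period for any pain item. An item asking about several days would be less noisy, and the gain from averaging would shrink.
- **That the result is biased towards one arm.** Baseline noise acts in the same way in both arms, and no minimum pain score is required for entry, so the criteria do not select on a high rating.

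It can also be said that this is a feasibility study with exploratory efficacy, and that the repeated-measures ANOVA does not use the 50% cut. Both are true and limit the severity. What remains is that the responder proportion is still named as the primary effectiveness measure. Two ratings help only if the plan says to average them, and with independent days and a five-session end mean, five ratings still did better than two at each true reduction tabulated.

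**Conclusion.** The point holds as a modest, inexpensive improvement. The plan provides no multi-day pain baseline for a within-subject 50% rule, and it leaves the pain instrument, the baseline value and the end window undefined. If one baseline rating were set against a five-session end mean, the baseline would contribute about 56% of the error variance at the cut. Five ratings would then lower false-responder calls at a true 30% reduction from about 13% to 6.6%, and missed responders at a true 60% reduction from about 27% to 20%.

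Those sizes rest on assumed variability, independence between days and a five-rating end value, none of which the documents supply. At autocorrelation 0.8 the gain is about 1 point or less. With a single end rating it is small overall and not uniform in direction. The consequence is lost precision and a blurred contrast between arms, not a tilt towards active or sham.

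**What to change.** Make these changes in the protocol before the first subject is treated:

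1. Name one pain item for the primary outcome and make sure it is on the schedule. Of the listed pain scales, only the BPI is rated before every session. If a VAS is intended, schedule it for pain.
2. Define baseline as the mean of all pre-stimulation ratings of that item: at minimum the baseline-visit and pre-session-1 ratings, preferably about five. Add the single item at the existing screening, MRI/MRS and motor-threshold contacts, or by phone, on separate days where possible.
3. Define the end value as the mean of the same item before the last five sessions.
4. State the item's recall period.

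The cost is about 5 − 2 = 3 extra single-item ratings per subject and a short definition in Statistical Analysis. The downside is slightly more burden before treatment. Since ratings precede sessions, the end mean would reflect 20 to 24 completed sessions and not all 25; the definition should say so.

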Specific Aim 1: Investigate the feasibility and tolerability of using rTMS on chronic pain in patients with opioid use disorder currently on methadone maintenance therapy and to investigate the effect of rTMS on chronic pain relief and substance use in an exploratory manner. Previous studies indicate that deep brain stimulation of the prefrontal cortex/anterior cingulate induces pain relief. Our hypothesis is that active rTMS, compared to sham, will improve pain after five weeks of treatment, thereby improving functional capacity and reducing opioid and other substance use.

Specific Aim 2: Investigation of the effect of rTMS using imaging. We will investigate target engagement with brain imaging. Magnetic resonance spectroscopy (MRS) will be used to measure changes in glutamate and vMRI to gauge changes in volume. Our hypothesis is that active rTMS will decrease glutamate levels and increase brain volume of the mPFC and ACC compared to sham.

Specific Aim 3: Investigation of the effect of rTMS on cognitive (i.e. executive) functioning in patients with chronic pain and opioid use disorder on methadone maintenance therapy. Previous studies have implicated a broad range of cognitive deficits in patients with substance use disorders, both during intoxication and withdrawal and after prolonged abstinence. Neuropsychological testing completed before and after rTMS treatment will be completed to determine if rTMS improves cognitive functioning, which may be a possible mechanism for improvement in chronic pain and/or opioid use disorder.

Background and Rational

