Chronic pain affects approximately 100 million Americans each year and costs an estimated \$560-\$635 billion annually, inclusive of health care expenses and lost productivity (Institute of Medicine Report from the Committee on Advancing Pain Research, Care, and Education, 2011). Aside from the economic cost, chronic pain is also associated with significant psychological and social consequences including anxiety, fear, depression, decline in social functioning and dependence on opioid analgesic (Institute of Medicine (US) Committee on Advancing Pain Research, Care, and Education, 2011). Furthermore, the lack of effective treatments for chronic pain is one factor that has contributed to the increase in opioid prescribing, and thus diversion, addiction, and overdoses in the U.S. Despite ongoing efforts to reduce opioid prescribing for chronic pain, an estimated 35% of all opioid prescriptions are for chronic pain, resulting in around 10 million American adults (3-4% of the population) receiving opioid treatment for this indication despite limited evidence of its effectiveness (Volkow, McLellan, et al, 2009; Boudreau , Von Korff, et al, 2009). In 2016, an estimated 11.8 million people in the U.S. (4.4% of the population) misused opioids, and 1.8 million (0.7% of the population) met DSM5 diagnostic criteria for an opioid use disorder (NSDUH 2017).

Recent imaging and neurophysiological evidence suggest that the dorsal anterior cingulate (dACC) plays an important role in the perception of pain (Russo et al, 2015, for review). Not only is the dACC involved in the cognition of pain but also the affective perception of pain, that is, the emotional valuation of pain. PET and fMRI studies have also demonstrated the dACC is involved in cognitive and affective pain perception.

Morphometric magnetic resonance imaging has shown decreases in the dACC in chronic pain patients (Russo et al, 2015, for review). Additionally, dACC dysfunction has been implicated in various substance use disorders, including opioid dependence (Yucel, Lubman, et al, 2007). Protocol Summary Form 7208 [name] Page 7 of 21 Advancements in the techniques of non-invasive brain stimulation such as repetitive transcranial magnetic stimulation (rTMS) have potential therapeutic effects for chronic pain and substance use disorder

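### As written, the Hamilton Anxiety scale and the opioid-craving VAS are scheduled only at 2 and 4 weeks after rTMS, with no stated baseline or end-of-treatment assessment

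*Combined protocol and SAP*

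**What the plan says.** The Post-treatment Follow-up section opens: "Participants will return at 2 weeks and 4 weeks after completion of rTMS for the following measures". Eleven numbered items follow. Item 1 is self-report of methadone changes and other substance use. Items 2 to 11 are rating scales; item 6 is the "Hamilton Anxiety Rating Scale" and item 11 is the "Visual Analogue Scale (VAS) for Opioid Craving". These are the only mentions of either scale.

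The scales for baseline, the treatment weeks and the end of rTMS are itemised under Neuropsychological scales and tests, beneath the line "Scales (expected to take 60 minutes total". There are 12, each with its own timing and each with a baseline. They include "Hamilton Depression Rating Scale (at baseline and weekly" and "Clinical Opiate Withdrawal Scale (COWS) (at baseline and weekly". Neither an anxiety scale nor a craving scale is among them.

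Specific Aim 1 sets out "to investigate the effect of rTMS on chronic pain relief and substance use in an exploratory manner". It names neither scale, and neither does the Statistical Analysis section.

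**The concern.** A scale first taken two weeks after treatment ends can show where participants are at that point, but not how they got there. If craving were low in both arms at week 2, nobody could say whether it had fallen, had always been low, or had been lower still when stimulation stopped. The same holds for anxiety.

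Both constructs bear on this population. Every participant has opioid use disorder and is on methadone. The background section describes chronic pain as associated with "significant psychological and social consequences including anxiety, fear, depression", so anxiety stands beside depression in the rationale, yet only depression is followed from baseline.

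The follow-up visits are also defined relative to completing rTMS. The section on early discontinuation provides for removing participants during treatment, and the document does not say whether they attend follow-up. Anyone who does not would contribute no value at all on these two scales.

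The stake is modest, but the loss is permanent: a pre-treatment value cannot be collected afterwards.

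**Working it through.** **Schedule check.** The ten follow-up rating scales (Post-treatment Follow-up, items 2 to 11) were compared with the 12-item list under Neuropsychological scales and tests.

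| Follow-up scale | Baseline stated? |
|---|---|
| Brief Pain Inventory | yes |
| PEG | yes |
| PROMIS-29 pain items | yes |
| Hamilton Depression | yes |
| Hamilton Anxiety | **no** |
| Patient-rated CGI | yes |
| Clinician-rated CGI | yes |
| CGI-opioid | yes |
| Q-LES-Q | yes |
| Opioid-craving VAS | **no** |

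Result: 8 of 10 have a stated baseline and 2 do not. For each of the two, the scheduled assessments are baseline 0, during treatment 0, end of treatment 0, follow-up 2.

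**Could they be covered elsewhere?** The eligibility tables, the Subject Screening section and the weekly assessments under Criteria for Early Discontinuation mention neither. No listed instrument stands in for them: COWS rates withdrawal rather than craving, Hamilton Depression is a different scale from Hamilton Anxiety, and the only other VAS in the document is the pain VAS in the primary outcome.

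**What can be estimated.** With values at weeks 2 and 4 only, the arms can be compared at each of those visits. Change from baseline, adjustment for baseline and any contrast at the end of treatment need values that are not scheduled.

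**Precision (illustrative only).** The document gives no sample size and no correlation *r* between baseline and follow-up scores, so both are assumed here. For equal precision, the number of participants needed without baseline adjustment, relative to the number needed with it, is about 1/(1 − r²) in large samples:

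- r = 0.3: 1/0.91 = 1.10
- r = 0.5: 1/0.75 = 1.33
- r = 0.7: 1/0.51 = 1.96

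In small trials, chance baseline imbalance takes back part of the gain, and the ratio is divided by 1 + 1/(2n − 4), with n per arm:

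- n = 10: factor 1 + 1/16 = 1.0625; ratios 1.03, 1.25, 1.85
- n = 20: factor 1 + 1/36 = 1.0278; ratios 1.07, 1.30, 1.91

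The gain vanishes when r² = 1 − 1/factor, which gives r of about 0.24 at n = 10 and 0.16 at n = 20. Below those values, adjustment does not improve precision.

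**Adjusted scores against change scores.** With equal variances, a change score has variance 2(1 − r) relative to 1.00 for the follow-up score alone: 1.40 at r = 0.3, 1.00 at r = 0.5, 0.60 at r = 0.7. Subtracting baseline therefore adds noise when r is below 0.5.

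**The case against.** The case for leaving this alone is fairly strong. The trial is described as a feasibility study. Neither scale enters the primary effectiveness outcome, the primary safety outcome, an aim or a specified analysis. Opioid use, COWS and CGI-opioid all have baselines. In a sham-controlled trial, the between-arm contrast carries the inference about treatment, and randomisation keeps that contrast valid at weeks 2 and 4. All of this stands, and it is why the point is minor.

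The scale list is also visibly incomplete. Baseline neuropsychological testing is promised but no cognitive test is itemised, and the pain VAS behind the primary outcome is not listed either. A reader might infer that the sponsor chose follow-up-only collection, or that no baseline will in fact be taken. The document supports only that none is stated.

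Two further inferences go too far:

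- A reader might conclude that the two scales are uninformative. They are not, because the arms can be compared at follow-up.
- A reader might take the upper ratios, near 2, as the sample-size cost of the omission. They rest wholly on assumed values of *r* and *n*, and at low *r* there is no cost in precision at all.

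Nor should the two scales be called exploratory outcomes on the document's authority: Aim 1 uses that word for pain relief and substance use, and the remark on anxiety in the background does not make anxiety an outcome.

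What survives is the gap in the schedule. With 8 of the 10 follow-up scales carrying a baseline and no reason given for the other two, an oversight is at least as plausible as a choice.

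**Conclusion.** The point holds as a minor one. As written, 2 of the 10 follow-up rating scales have no stated baseline or end-of-treatment assessment, so the plan cannot describe change in craving or anxiety within either arm, nor their level when treatment ended. The between-arm comparison at 2 and 4 weeks remains available and valid, without baseline adjustment.

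The count comes straight from the document and needs no assumption. The possible precision gain is illustrative: ratios from 1.03 to 1.96 over the assumed values, and none below the break-even correlations. The case for change rests mainly on interpretation. The primary outcome and the stated aims are unaffected.

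**What to change.** Add the Hamilton Anxiety scale and the opioid-craving VAS to the list under Neuropsychological scales and tests, at the existing baseline and after-completion assessments. State that any between-arm comparison of their follow-up scores will be adjusted for the baseline score (ANCOVA) rather than based on simple change scores. This needs saying because the Statistical Analysis section names only age, gender and ethnicity as candidate covariates. No new formal test is required; if the scales are only to be summarised, the added assessments still allow change to be described.

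If follow-up-only collection is intended, one sentence saying so, and that the two scales are descriptive, would remove the ambiguity. It would not supply the missing information.

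The cost is a schedule amendment and no new visit. Two more scales at two assessments lengthen a battery already expected to take 60 minutes. The document gives no completion time for either; a few minutes of participant and rater time is an assumption. The change helps only participants who have not yet started rTMS.

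### The primary effectiveness outcome is defined on a pain VAS that no visit schedules, and it is not tied to the time point and baselines given elsewhere in the protocol

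*Combined protocol and SAP*

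**What the plan says.** In the Combined protocol and SAP, Statistical Analysis, a responder must have at least a 50% "reduction in average pain score as measured by VAS and no significant increase in opioid medication use". A significant opioid increase is "defined as greater than 25% increase in morphine equivalent dose". The sentence states no visit, baseline or averaging window for either half.

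The Scales list covers baseline and treatment. Its pain entries are items 1 to 3:

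- "Brief Pain Inventory (at baseline and daily before each rTMS session"
- "PEG scale (at baseline and weekly before each rTMS session"
- "PROMIS-29 pain intensity and pain interference items (at baseline and weekly before each rTMS session"

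The Post-treatment Follow-up section opens with "Participants will return at 2 weeks and 4 weeks after completion of rTMS for the following measures". Its list repeats the same three pain instruments and ends with "Visual Analogue Scale (VAS) for Opioid Craving". Its opioid item is "Self-reported methadone dose adjustments/changes and other substance use".

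Timing is given in other places. Specific Aim 1 expects pain to improve by the end of the five-week course. The sentence that introduces the scales, under Neuropsychological scales and tests, has them completed at baseline and again once the course has finished. The Medication use paragraph labels the week before sessions as baseline and converts opioid use to daily oral morphine equivalents.

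**The concern.** A responder outcome needs a named score measured at least twice, once before treatment and once after. The outcome names a VAS, and the schedule offers no pain VAS at either time. The analyst would have to replace it with the BPI, the PEG or the PROMIS-29 pain items. The plan does not choose among these, so the choice could be made after results are known.

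The plan calls this the primary effectiveness outcome of a randomized sham comparison, and its Statistical Analysis section sets a two-tailed 0.05 threshold. If the score is settled later, readers cannot tell whether the reported responder proportion is the planned one. The unstated link to a time point and an opioid comparison period adds to that doubt, to a lesser degree.

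**Working it through.** The supplied text gives no sample size, response rate or power for this outcome, so there is no figure to reproduce. The check compares the outcome sentence with the schedule.

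**1. Is the named instrument scheduled?** The after-course column relies on the general sentence under Neuropsychological scales and tests, which covers the listed scales.

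| Measure | Baseline | During rTMS | After the course | 2 and 4 weeks later | Named in outcome |
|---|---|---|---|---|---|
| BPI | yes | before each session | yes | yes | no |
| PEG | yes | weekly | yes | yes | no |
| PROMIS-29 pain items | yes | weekly | yes | yes | no |
| Pain VAS | no | no | no | no | yes |
| Craving VAS | no | no | no | yes | no (not pain) |

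Pain VAS entries: 0 of 12 in the Scales list and 0 of 11 in the follow-up list, so 0 of 12 + 11 = 23. The abbreviation VAS occurs twice in the document, once in the outcome sentence and once for craving. Subject Screening mentions pain scales in general and names none. Both lists are numbered without gaps, so nothing suggests that a line was lost or blacked out.

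**2. Can the pain half be computed?** Percentage reduction = 100 × (baseline − later) / baseline. Both terms need a pain VAS and neither is scheduled. The craving VAS cannot stand in: it measures something else, and it has no listed baseline.

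**3. Is the time point recoverable?** Aim 1 points to the end of five weeks, and the general sentence gives a baseline and a post-course rating. The natural reading is change from the pre-treatment rating to the post-course rating. The outcome sentence does not say so, and the entries for the three pain scales show only the baseline and the daily or weekly ratings.

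**4. Is the opioid comparison recoverable?** The one period labelled as the medication baseline is the week before sessions, in the same paragraph as the conversion to morphine equivalents. The later comparison period is not stated, but data for it should exist. Five weeks × 5 days = 25 sessions, and each session asks about use since the previous one. With no missed sessions, session 20 falls on the Friday of week 4 and session 25 on the Friday of week 5. The reports at sessions 21 to 25 therefore cover the 7 days between them, the same length as the one-week baseline.

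**The case against.** The best defence is that this is a feasibility study, that Aim 1 studies pain relief as exploratory, and that pain is measured often, so the VAS wording is a drafting slip. Much of this stands. The lists do look incomplete: the text promises tests as well as scales but lists no cognitive test, and the follow-up list has two scales (Hamilton Anxiety and craving VAS) that the first list lacks. A slip is plausible. It still leaves the outcome without a usable instrument, and nothing in the text equates the VAS with a BPI item.

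The defence is stronger on timing and opioids. Several harsher readings are tempting, and the documents do not support them:

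- *No pain rating follows the full course.* A reader might infer this because the item entries list only pre-session ratings, which in week 5 come after 20 to 24 of the 25 sessions. The general sentence schedules the scales after completion, and the follow-up visits repeat the pain scales.
- *There are two rival opioid baselines.* Subject Screening does collect four weeks of daily medication use before study entry. That period is neither called a baseline nor tied to the morphine-equivalent conversion.
- *Opioid use after the last session is a serious gap.* The session questions cover the course up to session 25. Later days matter only if the window is made to end after that session.
- *The missing time point inflates the responder rate severalfold.* That would require counting a response on any occasion, which no section suggests, and response rates and correlations that the documents do not give.

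**Conclusion.** The point holds. The pain half of the labelled primary effectiveness outcome cannot be computed from the scheduled assessments: the named instrument is on 0 of 23 schedule entries, while three other pain instruments are scheduled and none is chosen. This rests on the two printed lists being the full schedule; no other section supplies a pain VAS.

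The timing and opioid part is secondary. The protocol is not silent on either. What is missing is a sentence that ties the outcome to the post-course rating, to the one-week medication baseline, and to a stated comparison week.

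A reader might go further and infer that a confirmatory result is compromised or that the trial collects no usable pain data. Neither follows. Aim 1 makes the pain effect exploratory, and pain data will exist. The damage is to the interpretability of the primary outcome, and no numerical bias can be derived from the documents.

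**What to change.** Amend the text before unblinding:

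1. In Statistical Analysis, replace the VAS with one pain score already collected at baseline and after treatment, for example the BPI average-pain score if that item is on the form used. If a pain VAS was intended, add it at baseline and after completion; that works only for participants not yet past baseline.
2. State that the reduction runs from the pre-treatment rating to the post-completion assessment, and show that assessment in the Scales entry for the chosen measure.
3. State that the 25% limit compares mean daily morphine equivalents in the week before sessions with the mean in the final treatment week, which the session-by-session tally already covers.
4. State how participants without the post-completion rating count, for example as non-responders. The early discontinuation criteria make such cases likely. Name the same pain measure in the repeated measures ANOVA, and make the other pain scales and the 2- and 4-week visits secondary.

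The cost is a short amendment with no new data collection. The VAS route adds one scale at two time points.
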